6.2.9 Electrocardiogram

12-lead electrocardiogram will be collected at visits 1 (prior to study drug administration) and 2 [at the end of study drug administration (when site personnel can gain access to the patient), within 4-6 hours and 12-24 hours post study drug administration], according to time and events (Section 15.0). The ECG will be evaluated for any abnormality and the following parameters will be recorded for each ECG: PR interval, RR interval, QRS complex time, QT interval and Corrected QT interval (QTc). Two copies of the ECG tracing will be produced. One copy is to be saved at the study site and the other copy to be sent to the independent central ECG reviewer (ACI Clinical, Bala Cynwyd, PA).

6.2.10 Clinical Laboratory Assessments

Safety laboratory investigations will include hematology (complete blood count including platelets and white cell differential), chemistry (Glucose; Electrolytes (Sodium, Potassium, Chloride, Bicarbonate); Renal function tests (Urea/BUN, Creatinine); Liver function tests (Albumin, Bilirubin Total, Alanine transaminase (ALT), Aspartate transaminase (AST), Alkaline phosphatase (ALP); Protein Total); Calcium; Phosphorus; CRP will be obtained during screening and at Day 14. Pregnancy testing will be done on all women of childbearing potential participating in the study, (using blood test or urine test whichever is faster). Those tests will be collected at intervals according to time and events Section 15.1

6.2.11 Immunogenicity

Blood (6 mL) for serum will be collected at screening, Days 14 and 29, and Month 3 visits for immunogenicity testing. The specific assay to test for immunogenicity against AB103 will be determined at the end of the trial. The study blood samples will be processed then aliquoted into three cryovials, flash frozen, stored in -70°C freezer prior to transport to the Central Lab. The study sites shall send all blood (serum) samples collected under this protocol to the Central Lab (see Laboratory Manual). The results of any analyses of the samples will be blinded to the study staff during the study and will not impact the medical management of the patient.

6.2.12 Biomarkers

Urine (5 mL) and blood (5 mL) for plasma will be collected for evaluations of biomarkers to assess AKI. The specific AKI biomarkers will be determined at the end of the trial. Numerous novel candidate protein AKI biomarker targets may be analyzed by immunoassay in the samples from the preliminary studies. Analyzed biomarkers may include novel targets not previously described in the literature as well as existing biomarkers, which will be measured for comparison. The study blood and urine samples will be processed, flash frozen, stored in -70 freezer prior to analysis. The results of any analyses of the samples will be blinded to the study staff during the study and will not impact the medical management of the patient. The study sites shall send all blood (plasma) and urine samples collected under this protocol to the Central Lab (see Laboratory Manual). The samples may be stored up to 5 years but will be used by the investigators only to identify and validate biomarker targets for assessment of at-risk patients and will not be used for any other purpose. Samples will be stored at the Central Lab. Any excess sample will not be individually identifiable.

6.2.13 RNA Expression

The purpose of the whole blood leukocyte transcriptome (RNA expression) profile testing is to obtain insight in the effect of AB103 on the host response to NSTI by detailed and unbiased analysis of the blood leukocyte response. For this, 5 mL of whole blood will be collected in 2 Paxgene tubes (PreAnalytix, Hombrechtikon, Switzerland; 2.5 mL per tube) before initiation of AB103 administration and at 4-6 hours, 24 hours, 72-96 hours and 7

days thereafter. At each of these time points whole blood leukocyte counts and differentials will be determined by the local laboratory. Genome-wide whole blood RNA expression profiling will be performed on the Affymetrix GeneTitan instrument using the U219 96-array microarray chip or equivalent. Samples may be stored for up to 5 years but will only be used for the evaluation of the effect of AB103 on host response to NSTI. Results will not be reported to the treating physician or the subjects (or their relatives). A detailed description of the collection, processing and storage of the samples can be found in a separate Laboratory Manual for the study.

6.2.14 Total blood volume collected

The total maximal volume of blood to be collected in the study is composed of study specific tests as well as tests that are part of the SoC. The list below represents the combined blood quantities. Less than a unit of blood (12.5 tablespoons) will be collected for each patient.

Visit	Туре	Maximal
		Volume (cc)
1 SCR	CRP	3
	Chemistry	4
	Hematology	4
	Arterial Blood Gas*	2
	Pregnancy test	2
	Blood Culture	20
	AKI Biomarker	5
	Blood leukocyte transcriptome profile	5
	Immunogenicity sample	6
	Total Volume	52
	Hematology (CBC with differential and platelets)	4
	Arterial Blood Gas*	2
2 Day 1	Creatinine & Hematology (For SOFA calculation 16-24h post study drug administration)	7
	Blood leukocyte transcriptome profile (4-6 hour post study drug administration sample)	5
	Total Volume	18
	AKI biomarker	5
3 Day 2	Blood leukocyte transcriptome profile	5
	Arterial Blood Gas*	2
	Chemistry (only Creatinine)	3
	Hematology (CBC with differential and platelets-)	4
5	Hematology (only platelet count)-obtain if full CBC to be done with	4
	transcriptome sample is not performed on same calendar day as	
	study Day 2	
	Total Volume	23
4 Day 3	Chemistry (only Creatinine)	3
	Hematology (CBC with differential and platelets-can be used for	4
	mSOFA data and for the transcriptome)	2
	Arterial Blood Gas*	2

Table 6: Maximal Blood Drawing by Visit

Visit	Туре	Maximal
		Volume (cc)
	Blood leukocyte transcriptome profile	5
	Total Volume	14
	Chemistry	4
	Hematology (CBC with differential and platelets)	4
5	Arterial Blood Gas*	2
Day 7	AKI biomarker	5
	Blood leukocyte transcriptome profile	5
	Total Volume	20
	Arterial Blood Gas*	2
6	Chemistry (only Creatinine)	3
Day 10	Hematology (Platelets only)	4
	Total Volume	9
	Arterial Blood Gas*	2
	CRP	3
7	Chemistry	4
Day 14	Hematology (CBC with differential and platelets)	4
	Immunogenicity sample	6
	Total Volume	19
8	Arterial Blood Gas*	2
Day 21	Chemistry (only Creatinine)	3
	Hematology (Platelets only)	4
	Total Volume	9
9	Arterial Blood Gas*	2
Day 29	Chemistry (only Creatinine & Albumin)	3
	Hematology (CBC with differential and platelets)	4
	Immunogenicity sample	6
	Total Volume	15
10	Chemistry (only Creatinine)	3
Month	Immunogenicity sample	6
3	Total Volume	9
Total Study		188

* Obtain ABG if clinically indicated. Otherwise record SpO2 value and also FiO2.

6.2.15 Microbiology

Microbiological testing will follow the SoC of treatment of NSTI patients. At the time of initial surgical exploration, and if surgical debridement is performed on study Day 3, a tissue sample will be cultured by the local microbiology laboratory.

The deep tissue specimens will be obtained at the time of the first debridement at the operating room at the study site medical center. Antibiotics received prior to the primary surgical debridement will be identified as well as antibiotics received during the study evaluation window of Days 1-28.

A specimen of infected tissue will be taken from the infected area, will be placed in a sterile container and transported by hand to the local designated clinical microbiology laboratory at the institution and according to the approved methods of each medical center. The specimens will then be processed as soon as possible by homogenization, the homogenate will be Gram stained, and cultured under 2 different conditions for testing of aerobic and anaerobic pathogens

Cultures of the NSTI wound will be obtained according to the schedule of events on Section 15.1. Bacterial isolates obtained from the patients in the study, and considered to be pathogens will be identified by genus and species using the methods established in the *Manual of Clinical Microbiology*⁴⁰. Results will be used to categorize patients according to microbiology organism group (Gram-positive, Gram-negative, anaerobic, mixed infection).

Susceptibility testing will be performed on all aerobic pathogens according to clinical laboratory standards institute (CLSI) criteria.

Blood culture for both aerobic and anaerobic bacteria will be taken during screening process. Repeat blood cultures for microbiology will also be obtained according to physician discretion, if the patient is suspected to have a new or progressive infection (if deterioration in the hospitalized patient's condition is observed (e.g. spiking a fever).

Bacterial isolates identified as *Streptococcus pyogenes* or *Staphylococcus aureus* will be stored frozen at the site and shipped to the Central Microbiology Laboratory (IHMA, Schaumburg, IL) for future testing. Instructions for freezing, storage and shipping of the bacterial isolates can be found in a separate Laboratory Manual for the study.

6.2.16 Use of additional rescue therapy

The following measures of medical rescue therapies will be recorded:

- Hyperbaric oxygen
- Corticosteroid use
- IVIG use
- Plasmapheresis

7. EVALUATION MEASURES FOR EFFICACY

7.1 Primary Efficacy Measures

To demonstrate the efficacy of AB103 as compared to placebo, in patients diagnosed with NSTI, using a clinical composite success endpoint:

The NSTI clinical composite score, NICCE will be defined as the primary end point which will be composed of the following patient outcomes (i) Alive at Day 28, (ii) Day 14 debridements \leq 3 (iii) No amputation done after the first debridement (iv) Day 14 modified SOFA (mSOFA) score \leq 1 (mSOFA includes respiratory, cardiovascular, CNS, renal, and hematologic organ components but not hepatic/liver component) (v) Reduction of \geq 3 score points between Baseline and Day 14 mSOFA score.

Conditional Co-Primary Efficacy Measure:

Modified clinical composite endpoint: Success is defined as meeting all 3 components of the composite score: Alive until Day 28, (ii) Day 14 debridements \leq 3 (iii) No amputation done after the first debridement (See Section 2.1 and Table 4).

7.2 Secondary Measures

- 5 component clinical composite endpoint but with mSOFA ≤ 1 at Days 21 and 28
- Distribution of mSOFA scores at Days 14 and 21
- Kaplan-Meier analysis of the time to resolution of mSOFA score to ≤1 with censoring at Day 14
- Single components of the composite end point
 - Alive at Day 28
 - Number of patients with debridements by Day $14 \le 3$
 - Number of amputations (excision to a joint space) (done after first debridement)
 - mSOFA score on Day $14 \le 1$
 - Reduction of \geq 3 score points between Baseline and Day 14 mSOFA score.
 - Critical care and hospital stay parameters, to be measured until Day 28
 - o ICU-free days
 - Days in ICU
 - Days on ventilator
 - Ventilator free days
 - Vasopressors days/ Vasopressors free days
 - Hospital length of stay (days)
- Clinical local parameters:
 - Number of debridement to days 7, 10, 14 and 28
 - Proportion of patients needing (up to Day 14):
 - 1. only one debridement to control the infection
 - 2. \geq 2 debridements to control the infection
 - 3. \geq 3 debridements to control the infection

- Clinical systemic parameters:
 - Evaluation of organ function over time, using mSOFA score
 - Recovery from AKI

7.3 Exploratory Measures:

- Evaluation of blood leukocyte transcriptome (RNA expression) profiling in patients with NSTI and compare genomic profile in patients treated with AB103 versus placebo
- Evaluation of the clinical response by baseline pathogen
- Evaluation of the microbiological outcome in the microbiological evaluable population
 - *By-Pathogen Bacteriological Response:* The by-pathogen bacteriological response for each causative organism identified at baseline (BL) will be defined as follows:
 - Eradication: BL causative organism cannot be isolated from any culture(s) obtained from a debridement performed on or after study Day 3.
 - Persistence: The BL causative pathogen is isolated from a debridement performed on or after study Day 3.
 - *By-Patient Bacteriological Response:* The by-patient bacteriological response will be determined according to the following definitions:
 - Eradication: All BL causative organism(s) have a response of Eradication.
 - Persistence: All or some BL causative organism(s) have a response of Persistence.
- Evaluation of plasma and urinary biomarkers in patients with AKI
- Data (including financially related data) will be gathered to evaluate possible health economic outcomes from the study, including but not limited to:
 - Length of stay (ICU and overall hospital)
 - Number of re-admissions
 - \circ Reduction in ICU admission rates (depending on patient population being selected i.e. severity of patients
 - Related to ICU admission the Sequential Organ Failure Assessment (SOFA) score is an important outcomes measure that should be incorporated into any health economics and outcomes research (HEOR) analysis
 - Relative reduction in any physical outcome (including in-hospital deaths)
- To evaluate NICCE outcome in screen failure patients with baseline mSOFA = 2 and post-operative mSOFA \ge 3
- Evaluation of the immunogenicity of AB103

8. EVALUATION CRITERIA FOR SAFETY

8.1 Primary Safety Measures

Measures throughout to Day 28: AEs (includes SAEs), clinical safety laboratory (through Day 14). Secondary infections and determination of survival. Specific times of these parameters are described in Schedule of Procedures, Appendix A, Section 15.1.

Timely, accurate, and complete reporting and analysis of safety information from clinical studies are crucial for the protection of patients, Investigators, and the Sponsor, and is mandated by regulatory agencies worldwide. The Sponsor or its affiliate has established SOP in conformity with worldwide regulatory requirements to ensure appropriate reporting of safety information; all clinical studies sponsored by Sponsor or its affiliates will be conducted in accordance with these procedures.

Patients (or their designee, if appropriate) must be provided with information indicating the name of the IMP, the study number, the Investigator's name and a 24-hour emergency contact number, and, if applicable, excluded concomitant medications.

8.2 Adverse Event Definitions and Classifications

The following definitions of terms are guided by the ICH and the United States Code of Federal Regulations [21 CFR § 312.32].

8.2.1 Adverse Event

An AE is any untoward medical occurrence in a patient or clinical investigation patient administered a pharmaceutical product and that does not necessarily have a causal relationship with this treatment. An AE could therefore be any unfavorable and unintended sign (including abnormal laboratory findings), symptom, or disease temporally associated with the use of an IMP, whether or not considered related to the IMP. This definition includes illnesses or injuries, and exacerbations of pre-existing conditions.

8.2.2 Serious Adverse Event

A serious adverse event (SAE) is an AE occurring during any study phase (i.e., treatment, follow-up), and at any dose of the IMP or placebo, that fulfils one or more of the following criteria:

- Results in death (for purposes of this trial deaths will be captured as clinical outcomes and only recorded as an SAE if deemed related to IMP)
- Is life-threatening (i.e., the patient was, in the opinion of the Investigator, at immediate risk of death from the event as it occurred)
- Requires or prolongs hospitalization
- Results in persistent or significant disability or incapacity (i.e., the event causes a substantial disruption of a person's ability to conduct normal life functions)
- Is a congenital anomaly or birth defect, or
- Is an important and significant medical event (e.g., allergic bronchospasm requiring intensive treatment in an emergency room or at home, blood dyscrasias or

convulsions that do not result in in-patient hospitalization, or the development of drug dependency or drug abuse) that, based upon appropriate medical judgment, may jeopardize the patient and/or may require medical or surgical intervention to prevent one of the other outcomes defining SAE.

8.2.3 Adverse Reaction

Any AE for which there is a reasonable possibility that the IMP caused the AE. "Reasonable possibility" means there is evidence to suggest a causal relationship between the IMP and the AE.

8.2.4 Expectedness of the Adverse Event

Expected adverse events are adverse events consistent with the applicable product information provided by the Sponsor (the Investigator's brochure for an investigational product). The Sponsor, in consultation with the medical monitor, determines expectedness. If a SAE is **expected** no further action is required. If the Sponsor and medical monitor determine that SAE is **unexpected**, then the event may meet criteria for expedited SAE notification to the regulatory agencies.

8.2.5 Serious and Unexpected Suspected Adverse Reaction (SUSAR)

An adverse reaction that is both unexpected (not consistent with the observed or expected risk information applicable to the IMP) and also meets the definition of "serious" described above. All 3 of the definitions contained in the FDA requirement for expedited reporting must be met to qualify for expedited reporting to FDA: 1) Serious, 2) Unexpected, and 3) Suspected AR. AEs that do not meet the requirements for expedited reporting will be reported to FDA in the IND Annual Report. SUSARs that are fatal or life-threatening will be reported to FDA as soon as possible, but no later than 7 calendar days after Sponsor's initial receipt of the information (21 CFR 312.32(c)(2)). Other SUSARs will be reported to FDA within 15 calendar days of initial receipt or after determining that the information qualifies for reporting under 21 CFR 312.32(c)(1).

8.2.6 Adverse Events Based on Examinations and Tests

Deterioration as compared to baseline in protocol mandated laboratory values, vital signs and other safety variables should only be reported as AEs if they fulfil any of the SAE criteria or are the reason for discontinuation of treatment with the IMP. However, the Investigator may record such findings as an AE at his/her discretion in addition to completing an unscheduled laboratory/vital signs page with the information on the clinically significant test abnormality. If a deterioration in a laboratory value/vital sign is associated with clinical signs and symptoms, the sign/symptom will be reported as an AE and the associated laboratory result/vital sign will be considered as additional information. Any new or aggravated clinically relevant abnormal medical finding at a PE, dermal examination or lung auscultation as compared with the baseline assessment will be reported as an AE. Clinically relevant deterioration in unscheduled assessments of laboratory/vital signs/ECG parameters should be reported on additional eCRF pages.

Wherever possible, the reporting Investigator uses the higher level medical concept, rather than the laboratory term (e.g., anemia versus low hemoglobin value).

8.2.7 Pregnancies

If pregnancy is detected after the administration of study drug, the patient will be followedup until resolution. The Investigator must immediately record the pregnancy on the pregnancy reporting form and notify Sponsor/designee Pharmacovigilance by telephone and fax form within 24 hours of becoming aware of the event. In addition, the Investigator must report follow-up information regarding the course of the pregnancy, including perinatal and neonatal outcome.

If pregnancy is reported in a female partner of a male patient, the female partner will be asked to sign a separate consent form to allow the site personnel to capture data about the pregnancy and to follow the pregnancy until completion. No information about such pregnancies will be captured without informed consent from the female partner.

8.2.8 Relationship to Investigational Medicinal Product

The relationship of an AE to the administration of IMP (unrelated, probable or definite) is a clinical decision based on all available information at the time of the completion of the eCRF.

IMP relationship will be evaluated according to the following definitions:

Unrelated: includes the existence of a clear alternative explanation (e.g., mechanical bleeding at surgical site) or non-plausibility (e.g., the patient is struck by an automobile, at least where there is no indication that the IMP caused disorientation that may have led to the event; cancer developing a few days after IMP administration).

Probable: The AE, including clinical laboratory abnormality, follows a reasonable sequence from the time of IMP administration, follows a known response pattern of the IMP class, is unlikely to be attributed to the patient's clinical state, and is confirmed by improvement on stopping the IMP (de-challenge).

Definite: The AE, including clinical laboratory abnormality, follows a plausible sequence from the time of IMP (or placebo) administration; follows a known or expected response pattern to the IMP class; cannot be explained by disease or it disappears or decreases on cessation or reduction in IMP dose; and/or it reappears or worsens when the IMP is readministered.

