5.4.1 Study Drug - AB103

5.4.1.1 Precautions

Currently available safety information does not require any special precautions to be exercised during treatment with AB103. Analysis of safety data collected in AB103 Phase 1 and 2 studies, did not reveal AEs that were determined as related to AB103 (including

possibly, probably and definitely related to study drug). In animal toxicology studies no target organs were identified.

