9.1.1 Summary of adverse events

All analyses of adverse events will be based on the As Treated (Safety) Analysis Set. A summary of the numbers and percentages of patients within each treatment group experiencing at least one treatment emergent adverse event (TEAE) will be provided in Table 14.3.1.1. TEAEs will be defined as an AE occurring from Day 1 to end of study which is defined as Day 28. 'Drugrelated' is defined as 'possibly', 'probably', or 'definitely' caused by the study medication.

The AE endpoints summarized in this table are:

- With one or more TEAE
- With one or more drug-related TEAE
- With one or more serious TEAEs
- With one or more serious drug-related TEAE
- With one or more severe TEAE
- With one or more moderate or severe TEAE
- TEAE with outcome of death
- TEAE with outcome of drug related death
- Discontinued study drug due to AE/SAE
- Discontinued from study due to AE/SAE

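### The protocol's causality scale has no 'possible' level and a de-challenge condition ill suited to a single infusion, so it does not match the SAP's definition of drug-related

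*Protocol*

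**What the plan says.** Protocol 8.2.8 gives three levels: "The relationship of an AE to the administration of IMP (unrelated, probable or definite) is a clinical decision". *Unrelated* is described by a clear other cause or by implausibility. *Probable* joins four conditions: a reasonable time sequence, a known response pattern of the class, a low likelihood that the patient's condition explains the event, and that the event "is confirmed by improvement on stopping the IMP (de-challenge". *Definite* needs a plausible sequence and a known or expected class pattern, and that the event "cannot be explained by disease or it disappears or decreases on cessation or reduction in IMP dose". Re-appearance on re-administration is attached with 'and/or'.

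Three other places use a different threshold:

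- SAP 9.1.1: drug-related "is defined as 'possibly', 'probably', or 'definitely' caused by the study medication".
- Protocol 8.2.3: an adverse reaction is an event for which causation by the product is a reasonable possibility.
- Protocol 5.4.1.1, on the Phase 1 and 2 data: no events were found to be related, where related covers "possibly, probably and definitely related to study drug".

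Treatment is one infusion over 10 minutes (protocol 5.1.1). Protocol 1.1.3.3.1 gives a half-life of a little over one minute in healthy volunteers.

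**The concern.** The grade recorded under 8.2.8 is the natural source for every output that the SAP calls drug-related. If the scale cannot record the lowest degree of suspicion, that degree is missing from those outputs in both arms. No later programming can restore it. The rule in SAP section 1 that the SAP prevails over the protocol does not help, because it cannot supply a grade that was never collected.

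The population makes this more than a formality. In critically ill patients with necrotizing infection, many events will have the disease as a possible contributor, and that is what a *possible* level is for. SAP 1.1 adds that this trial will form most of the safety population for the NDA, so a narrow relatedness scale would carry into the integrated safety summary.

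**Working it through.** No numerical figure in the plan bears on this point, so the check applies the written definitions as rules.

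**Step 1: levels.** SAP drug-related = possibly + probably + definitely, which is 3 levels. Related levels in protocol 8.2.8 = probable + definite, which is 2. So 3 − 2 = 1 SAP level has no source in the protocol scale.

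**Step 2: which events fit which level.** Take an event with a plausible time sequence for which neither de-challenge nor re-challenge can be assessed. This is the usual situation for an event that starts after a completed 10-minute infusion of a drug with so short a half-life. Cross the class pattern (2 states) with the disease as an explanation (4 states), giving 2 × 4 = 8 cases. I read the conditions for *definite* as cumulative, with re-challenge optional.

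| Disease as explanation | Class pattern known (or, for definite, expected) | No such pattern |
|---|---|---|
| Clear alternative explanation | unrelated | unrelated |
| Possible contributor | no level fits | no level fits |
| Unlikely | no level fits | no level fits |
| Cannot explain the event | definite | no level fits |

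Count: 2 unrelated + 1 definite + 0 probable + 5 fitting no level = 8.

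**Step 3: the more generous reading.** Suppose that an event which abates when the infusion ends or is interrupted counts as a positive de-challenge. *Probable* can then be reached in the 'unlikely' row of the known-pattern column. Relief on cessation is also an alternative route to *definite*, so the possible-contributor case in that column can meet *definite*. The right-hand column does not change. Both related levels require the pattern, so 3 of its 4 cases still fit no level. That column matters here because 5.4.1.1 reports no related events from which a pattern could be known.

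**Step 4: order of the levels.** De-challenge is compulsory for *probable* but only one alternative for *definite*. On that condition the stronger grade is the easier one to reach.

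**Step 5: outputs that use the grade.** These are Tables 14.3.1.4, 14.3.1.7, 14.3.1.10 and 14.3.1.11 and the drug-related rows of 14.3.1.1. SAP 9.1.2 also describes Table 14.3.1.5 as drug-related, but SAP Appendix 1 titles it as all serious events, and I have followed the appendix. Table 14.3.1.12 is produced only if at least 5 subjects have a drug-related event (SAP 9.1.4), so under-grading could remove it.

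**The case against.** The case for leaving this alone has several sound parts.

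- **Events are not forced into *unrelated*.** A reader might infer that they are. Protocol 8.2.8 ties that level to a clear other cause or to implausibility and calls the grade a clinical decision on all the information available. A plausible event does not meet that description. It meets none of the three. Grading it unrelated is a likely default, not a stated rule. This objection stands.
- ***Probable* is not empty by construction.** An infusion can be interrupted. Protocol 8.2.9 and 8.5 and a row in SAP 9.1.1 all allow for discontinuation of study drug, and an event may subside as the infusion ends. This also stands, within the limits shown in step 3.
- **The tables can be produced.** The SAP definition is a union, so the programs run on probable plus definite events. The tables are narrower than defined, not impossible to fill.
- **The eCRF is not among the documents.** If its list includes *possible*, the fault lies in the protocol text alone. Even then, 8.2.8 would still tell investigators that the option does not exist.
- **The main safety comparison does not need relatedness.** The randomized comparison of all events, serious events, severe events and infections is the stronger evidence, and the iDMC sees safety data unblinded by group (protocol 8.7). This limits the importance of the point but does not remove the contradiction between the two documents.

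**Conclusion.** The point holds. Protocol 8.2.3, protocol 8.2.8 and SAP 9.1.1 set different thresholds for a related event, and the one used for grading is the strictest. One of the SAP's three drug-related levels has no source. Where de-challenge cannot be assessed, 5 of the 8 event types in the grid fit no written level. The grid counts types, not patients. The documents give no basis for estimating how many events would be lost.

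The effect is confined to the drug-related TEAE outputs listed in step 5. All-cause, serious and severe TEAE tables, mortality analyses and efficacy are not affected. The point should be fixed, but it does not threaten the trial's main conclusions.

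Three stronger readings are not supported:

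- **SUSAR reporting.** A reader might infer that the scale decides it. Protocol 8.2.5 requires a suspected adverse reaction, which 8.2.3 defines by reasonable possibility. Neither refers to the levels in 8.2.8.
- **Deaths.** Under protocol 8.2.2, "deaths will be captured as clinical outcomes and only recorded as an SAE if deemed related to IMP", so a reader might infer that deaths disappear. That sentence does not cite the 8.2.8 scale. Deaths are captured in any case in the primary endpoint, the life tables to Day 90 (SAP 9.6) and the Death Form listing.
- **Comparability with Phases 1 and 2.** The wording in 5.4.1.1 suggests that the earlier scale had a *possible* level. The earlier scales themselves are not in the documents, so non-comparability is not shown.

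The verdict assumes that relatedness is graded as 8.2.8 is written and that the SAP tables draw on that grade.

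**What to change.** Reconcile protocol 8.2.3, protocol 8.2.8 and SAP 9.1.1:

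1. Add a *possible* level to 8.2.8, for an event with a reasonable time sequence that the patient's condition could also explain. SAP 9.1.1 can then stay as it is.
2. State that the de-challenge, dose-reduction and re-challenge conditions are not applicable when they cannot be assessed after a single dose.
3. Check the eCRF list and add *possible* if it is absent.
4. Re-query relatedness for events already coded, while treatment allocation is still blinded.

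The cost is protocol wording, at most one eCRF value and some re-query work at sites. More events will be labelled drug-related, in both arms. Patient management does not change. Timing matters, because a re-grading done after unblinding would carry little weight.
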